ARQ-151-202 Amendment 1 April 12, 2019	
 • Added protocol revision history section • Updated Sponsor address • Added I-IGA and mPASI to secondary endpoints throughout • Added Cohort 2 (non ARQ-151-201) subjects throughout • Added phone visits at Weeks 18, 30 and 44 and added instructions for the subject to call the site prior to restarting study medication • Added additional inclusion and exclusion criteria for Cohorts 1 and 2 • Updated exclusion criteria to exclude moderate to severe liver impairment (Child-Pugh B or C) • Added Screening visit for non-ARQ-151-201 subjects including the Screening C-SSRS • Added Table 2, Wash out period for Medications and Treatments for Cohort 2 • Added Appendix 1 Columbia-Suicide Severity Rating Scale (C-SSRS) Baseline/Screening Version • Updated Columbia-Suicide Severity Rating Scale (C-SSRS) Since Last Visit Version to Appendix 2 and updated National Institute of Allergy and Infectious Diseases, Division of Microbiology and Infectious Diseases (DMID) Toxicity Table for Use in Trials Enrolling Healthy Adults (2014) Modified to Appendix 3 • Editorial and administrative changes throughout the protocol to clarify language and formatting to improve readability.

4 SYNOPSIS

Compound	ARQ-151 cream 0.3%
IND	135,681
Clinical Indication	Chronic Plaque Psoriasis
Study Phase and Type	
 Phase 2 (2b) 52 week, long-term safety study of ARQ-151 cream 0.3%
Study Objectives	To assess long-term safety in a multicenter, open-label, 52-week study in subjects treated with ARQ-151 cream 0.3% after completing a 12-week Phase 2b study (ARQ-151-201) Cohort 1 and non-ARQ-151-201 subjects (Cohort 2).
Study Endpoints	
Primary Endpoints
 
 Occurrence of treatment emergent AEs (TEAEs) Occurrence of Serious Adverse Events (SAEs) 
Secondary Endpoints
 
 Proportion (%) of subjects achieving an Investigator Global Assessment (IGA) of clear or almost clear, as observed at Week 12 and subsequent scheduled visits. Proportion (%) of subjects who achieve 'clear' IGA, I-IGA (if applicable) and mPASI (Modified Psoriasis Area Severity Index) score and stop treatment to all lesions, time to re-starting study drug (duration of response). Proportion (%) of applicable subjects with intertriginous area involvement, 'I-IGA' score of 'clear' or 'almost clear' at week 12 and subsequent visits. Proportion of subjects who achieve a 75% reduction in mPASI at Week 12 and subsequent scheduled visits as compared to baseline.
Summary of Study Design	Open-label, long-term safety study of ARQ-151 cream 0.3% in subjects with chronic plaque psoriasis involving up to 25% total BSA. Cohort 1 eligible subjects will enroll into the long-term safety study on the same day as the Week 12 visit for the previous study (ARQ-151-201). Cohort 2 eligible subjects will enroll on Day 1 of this study. Study medication will be applied by the qualifying subjects topically QD for 52 weeks at home. Periodic clinic visits will include assessments for clinical safety, application site reactions evaluated in the clinic using the method of Berger and Bowman, and disease improvement or progression.

Blinding	
 • This study is open label • All participants will receive ARQ-151 cream 0.3%
Countries:	United States and Canada
Number of sites	Approximately 30 sites
Study Population	Subjects who have completed the 12 week treatment period in study ARQ-151-201 and are willing to enroll in this 52-week extension study (Cohort 1) and qualified non-ARQ-151-201 subjects (Cohort 2).
Inclusion Criteria All Subjects	
 1. Participants legally competent to sign and give informed consent 2. Males and females ages 18 years and older 3. Females of childbearing potential (FOCBP) must have a negative urine pregnancy test at all study visits. In addition, sexually active FOCBP must agree to use at least one form of highly effective contraception throughout the trial. Highly effective forms of contraception include: oral/implant/injectable/transdermal contraceptives, intrauterine device, or partner's vasectomy. If barrier methods are used (e.g., condom with spermicide, diaphragm with spermicide), then 2 forms of conception are required. The use of abstinence as a contraceptive measure is acceptable as long as this is a consistent part of a lifestyle choice and a backup method has been identified if the subject becomes sexually active. 4. Post-menopausal women with spontaneous amenorrhea for at least 12 months or have undergone surgical sterilization (permanent sterilization methods include hysterectomy, bilateral oophorectomy, hysteroscopic sterilization, bilateral tubal ligation or bilateral salpingectomy).
Inclusion Criteria Cohort 1 Only	
 5. Subjects with chronic plaque psoriasis who met eligibility criteria for ARQ-151-201, successfully completed ARQ-151-201 through Week 12, and are able to enroll into this long-term safety study on the Week 12 visit of the previous study (ARQ-151-201).
Inclusion Criteria Cohort 2 Only	
 6. Clinical diagnosis of psoriasis vulgaris of at least 6 months duration as determined by the Investigator. 7. Psoriasis vulgaris on the face, extremities, trunk, and/or intertriginous areas involving 2% to 25% of BSA (excluding the scalp, palms and soles). 8. An Investigator's Global Assessment of disease severity (IGA) of at least Mild ('2') at Day 1.
Exclusion Criteria All Subjects	
 1. Subjects that use any Excluded Medications and Treatments (see Table 1). 2. Subjects currently taking lithium or antimalarial drugs. 3. Planned initiation or changes to concomitant medication that could,

	
in the opinion of the Investigator, affect psoriasis vulgaris (e.g. beta blockers, ACE inhibitors).
 
4. Current diagnosis of guttate, erythrodermic/exfoliative, palmoplantar, or pustular psoriasis.
 
5. Subjects with any condition on the treatment area which, in the opinion of the Investigator, could confound safety or efficacy measurements.
 
6. Known allergies to excipients in ARQ-151 cream [REDACTED] [REDACTED]
 
7. Subjects who cannot discontinue the use of strong P-450 cytochrome inhibitors e.g., indinavir, nelfinavir, ritonavir, clarithromycin, itraconazole, ketoconazole, nefazodone, saquinavir, suboxone and telithromycin during the study period.
 
8. Subjects who cannot discontinue the use of strong P-450 cytochrome inducers e.g., efavirenz, nevirapine, glucocorticoids, barbiturates (including phenobarbital), phenytoin, and rifampin during the study period.
 
9. Subjects who have received oral roflumilast (Daxas®, Daliresp®) within the past 4 weeks.
 
10. Known or suspected:
 
• severe renal insufficiency or moderate to severe liver impairment (Child-Pugh B or C)• hypersensitivity to component(s) of the investigational products• history of severe depression, suicidal ideation 
11. Females who are pregnant, wishing to become pregnant during the study, or are breast-feeding.
 
12. Subjects with any serious medical condition or laboratory abnormality that would prevent study participation or place the subject at significant risk, as determined by the Investigator.
 
13. Subjects with a history of chronic alcohol or drug abuse within 6 months of initiation of study medication.
 
14. History of and/or concurrent condition of serious hypersensitivity (anaphylactic shock or anaphylactoid reaction) to PDE-4 inhibitors.
 
15. Current or a history of cancer within 5 years with the exception of fully treated skin basal cell carcinoma, cutaneous squamous cell carcinoma or carcinoma in situ of the cervix.

--	---

	16. Subjects who are unable to communicate, read or understand the local language, or who display another condition, which in the Investigator's opinion, makes them unsuitable for clinical study participation.
Exclusion Criteria Cohort 1 Only	17. Subjects who experienced an ARQ-151 treatment-related AE or a serious AE (SAE) that precluded further treatment with ARQ-151 cream in Study ARQ-151-201.
Exclusion Criteria Cohort 2 Only	18. Subjects who cannot discontinue medication and treatments prior to the Day 1 visit according to Excluded Medications and Treatments (Table 2).
Number of Subjects	Up to approximately 300 subjects (Cohort 1) Up to approximately 100 subjects (Cohort 2)
Duration of Participation for Subjects	Approximately 52 weeks
Study Products	ARQ-151 drug product will be supplied as a 0.3% cream in a squeezable tube.
Planned Dose Level	
 Subjects with up to 25% total BSA of psoriatic lesions will receive ARQ-151 cream 0.3% to be applied QD topically to all lesions. Application will be to all areas affected including the face and intertriginous/genital regions (except for the scalp). Subjects may stop treatment to lesions/areas that have cleared and completely resolved. Treatment may resume in these or new areas should psoriatic lesions emerge during the study. If treatment is judged by the Investigator as being ineffective, then the subject may be withdrawn from the study at any time.
Safety Assessments	Safety will be monitored through application site assessments in the clinic using the method of Berger and Bowman, clinical laboratory testing, 12-lead ECGs, PHQ-8, C-SSRS and AEs.
Safety Analysis	
Adverse Events
 
A subject-by-subject treatment-emergent AE (TEAE) data listing, including verbatim term, preferred term, treatment, severity, and relationship to study drug, will be provided.
 
The number of subjects experiencing AEs and number of AEs will be summarized by treatment using frequency counts.
 
Physical Examinations
 
Vital signs will be collected at all study visits. Physical examinations and 12-lead ECGs will be collected periodically throughout the study.
 
Clinical Laboratory Results
 
Routine blood chemistries will be obtained at all study visits. Urine

	
pregnancy tests will be collected periodically throughout the study.
 
Patient Health Questionnaires
 
PHQ-8 and C-SSRS questionnaires will be completed by the subjects at all study visits. Descriptive statistics will be calculated for the PHQ-8. The C-SSRS will be analyzed per the Scoring and Data Analysis Guide from the Columbia Lighthouse Project.

Efficacy Analysis	
The efficacy endpoints will be defined as:
 
 • Proportion (%) of subjects achieving an Investigator Global Assessment (IGA) of clear or almost clear, as observed at Week 12 and subsequent scheduled visits. • In subjects who achieve 'clear' IGA, I-IGA and MPASI scores and stop treatment to all lesions, time to re-starting study drug (duration of response) • Proportion (%) of applicable subjects with intertriginous area involvement, 'I-IGA' score of 'clear' or 'almost clear' at week 12 and subsequent visits • Proportion (%) of subjects achieving a 75% reduction from Baseline of Modified Psoriasis Area Severity Index-75 (mPASI-75) at weeks 12, 24, 36 and 52 as compared to Baseline.
Power and Sample Size	
Up to approximately 300 subjects are planned for Cohort 1 and up to approximately 100 subjects are planned for Cohort 2.
 
The sample size will provide a sufficient population size to evaluate the long-term safety of ARQ-151 cream 0.3% at 52 weeks.

Statistical Analysis:	
This study is not intended to assess efficacy, but rather the IGA, I-IGA and mPASI are included to determine the need for treatment and subsequent re-treatment after treatment course in Study ARQ-151-201 or Study ARQ-151-202. Certain efficacy data and endpoints will, however, be summarized.
 
Descriptive statistics will be presented for the endpoint data collected in the clinical trial. For analysis of the proportion (%) of subjects achieving an IGA of clear or almost clear at week 52, as observed, no imputation for missing data will be performed. The proportion of successes for the secondary variables of I-IGA and 75% reduction in mPASI will be tabulated.
 
The duration of response will be analyzed using the Kaplan-Meier method.
 
No formal inferential statistics will be performed on safety assessments. Descriptive statistics will be calculated for quantitative safety data and frequency counts will be compiled for classification of qualitative safety data.

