8.2.2 Secondary Endpoints

The secondary endpoints are related to efficacy and will include:

- Proportion (%) of subjects achieving an Investigator Global Assessment (IGA) of clear or almost clear, as observed at Week 12 and subsequent scheduled visits.
- In subjects who achieve 'clear' scores for IGA, I-IGA (if applicable **and** mPASI (Modified Psoriasis Area Severity Index) and stop treatment to all lesions, time to re-starting study drug (duration of response).
- Proportion (%) of applicable subjects with intertriginous area involvement, 'I-IGA' score of 'clear' or 'almost clear' at week 12 and subsequent visits
- Proportion (%) of subjects achieving a 75% reduction from Baseline of Modified Psoriasis Area Severity Index-75 (mPASI-75) at weeks 12, 24, 36 and 52 as compared to Baseline.

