9.6.3 Removal of Subjects from the Study

Subject participation in this trial may be discontinued for any of the following reasons:

1. Occurrence of any medical condition or circumstance that, in the opinion of the Investigator, exposes the subject to substantial risk and/or does not allow the subject to adhere to the requirements of the Protocol.
2. Occurrence of a treatment-emergent adverse event (TEAE) or considerable worsening of an AE that, in the opinion of the investigator in consultation with the Medical Monitor and

Sponsor, represents an unacceptable risk to the subject if he/she continues in the study. The investigator must follow the subject until the AE resolves or satisfactorily stabilizes.

3. Pregnancy.
4. Subject's decision to withdraw.
5. Weight loss of >5% if not dieting or intentionally trying to lose weight and after consultation with the Sponsor, at the Investigator's discretion.
6. C-SSRS indicative of suicidal ideation or a PHQ-8 score ≥ 15 , after consultation with a mental health professional, the Sponsor, and at the Investigator's discretion.
7. Requirement for use of prohibited concomitant medication.
8. Subject's repeated failure to comply with protocol requirements or study related procedures.
9. Termination of the study by the Sponsor, FDA, or other regulatory authorities.

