11.1 Statistical Methods

The methodology presented below is a summary of the more detailed analysis plan that will be presented in the Statistical Analysis Plan (SAP). The SAP will be finalized before the database is locked and unblinded. Any changes to the methods described in the final SAP will be described and justified in the clinical study report.

All statistical processing will be performed using SAS[®] (Version 9.4) unless otherwise stated. No interim efficacy analyses are planned.

Descriptive statistics will be used to provide an overview of the safety and efficacy results. For categorical parameters, the number and percentage of subjects in each category will be presented. The denominator for percentage will be based on the number of subjects appropriate for the purpose of analysis. For continuous parameters, descriptive statistics will include n (number of subjects), mean, standard deviation (SD), median, minimum, and maximum.

Missing efficacy and/or safety data will remain missing and will not be estimated.

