11.1.3 Subjects to Analyze

All analyses will be performed using the Safety Population which includes all subjects who are enrolled and received at least one confirmed dose of ARQ-151 cream 0.15% or ARQ-151 cream 0.3% study medication either in the Phase 2b Study (ARQ-151-201) or this extension study (ARQ-151-202). The number of patients included in the Safety Population will be summarized.

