11.3 Efficacy Evaluation

This study is not intended to assess efficacy, but rather the IGA, I-IGA and mPASI are included to determine the need for treatment and subsequent re-treatment after treatment course in Study ARQ-151-201 or Study ARQ-151-202. Certain efficacy data and endpoints will, however, be summarized.

Descriptive statistics will be used to summarize the assessment of efficacy. IGA scores will be summarized at Baseline Visit of Study ARQ-151-201 and every scheduled visit through end of the study (Day 1 and Weeks 4, 12, 24, 36, and 52). The efficacy variable in this study is success in Investigator Global Assessment (IGA) of disease severity, defined as an IGA of 'Clear' or 'Almost Clear'. The number and percentage of patients who achieve treatment success at the scheduled study visits will be tabulated. The proportion of successes for the secondary variables of I-IGA and 75% reduction in mPASI will be tabulated in a similar manner.

The number of treatment free days until the first retreatment (relapse) will be calculated and analyzed. For rollover subjects previously treated with Vehicle Cream, the number of treatment free days will be the number of days between the end of the initial treatment in study ARQ-151-202 and the start of the next treatment in study ARQ-151-202 if one should be needed or the end of the subject's participation in study ARQ-151-202. For rollover subjects previously treated

with ARQ-151 cream 0.3% or ARQ-151 cream 0.15%, the number of treatment free days will be the number of days between the last treatment that began in Study ARQ-151-201 and the start of the next treatment in study ARQ-151-202 if one should be needed or the end of the subject's participation in the study ARQ-151-202. There may be additional analyses comparing subjects that were previously treated with ARQ-151 cream 0.3% and ARQ-151 cream 0.15% in the ARQ-151-201 study.

Descriptive statistics for retreatment rates will be presented. The time (number of days) to relapse will be analyzed using the Kaplan–Meier method. The median time to relapse will be calculated in addition to other appropriate descriptive statistics. Patients who discontinue study ARQ-151-202 without relapse will be considered censored in the Kaplan–Meier analysis.

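### Late IGA, I-IGA and mPASI-75 success rates leave missing data missing while the protocol permits outcome-related withdrawal, so they are liable to be overstated

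*Protocol*

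**What the plan says.** **Missing data.** The Synopsis (Section 4, Statistical Analysis) says of IGA success at Week 52: "as observed, no imputation for missing data will be performed". Section 8.2.2 defines the IGA endpoint "as observed at Week 12 and subsequent scheduled visits". Section 11.1 covers everything else: "Missing efficacy and/or safety data will remain missing and will not be estimated". Section 11.3 adds: "The proportion of successes for the secondary variables of I-IGA and 75% reduction in mPASI will be tabulated in a similar manner".

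**Exits.** The Synopsis (Planned Dose Level) states: "If treatment is judged by the Investigator as being ineffective, then the subject may be withdrawn from the study at any time". Section 9.6.3 does not list ineffectiveness among the grounds for removal, but does list "Requirement for use of prohibited concomitant medication". Table 1 in Section 9.7.1 shows that the prohibited treatments include other topical and systemic psoriasis therapies and phototherapy.

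**Denominator and tallying.** Section 11.1 says: "The denominator for percentage will be based on the number of subjects appropriate for the purpose of analysis". Section 11.1.3 says: "All analyses will be performed using the Safety Population". Section 10.5 leaves the rules for tallying categorical responses to the SAP, which is not at hand. Section 10.4 gives withdrawn subjects a termination visit with the final-visit assessments.

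**Role of efficacy.** The Synopsis and Section 11.3 state that the study is not meant to assess efficacy. The responder proportions are listed secondary endpoints and will be summarised descriptively.

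**The concern.** Under an as-observed rule, a subject who has left contributes nothing to later visits. That does no harm if those who leave would have responded like those who stay. Here the protocol itself provides exits that follow from poor response: investigator withdrawal for ineffectiveness, and removal when other psoriasis treatment is needed. A flare also counts as an adverse event (Section 10.1.8), and an adverse event can lead to removal (Section 9.6.3). If such exits are used, non-responders are under-represented at Weeks 24, 36 and 52.

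There is no control arm to show how much of a flat or rising success rate comes from retention. A reader could take selective attendance for durable response over 52 weeks. The relapse analysis in Section 11.3 has a stated rule for subjects who discontinue (censoring); the responder proportions have no counterpart beyond leaving the data missing.

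**Working it through.** The protocol gives no response rate, dropout rate or effect size, so there is no figure of its own to reproduce. The check has two parts.

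**1. Which endpoints does the rule reach?**
- IGA, Week 12 onward: as observed, directly from Section 8.2.2. The explicit no-imputation sentence in the Synopsis names IGA at Week 52 only.
- I-IGA and mPASI-75: not covered by that sentence. They are reached through Section 11.1 (missing efficacy data stay missing) together with Section 11.3 (tabulated like IGA).

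**2. How large can the effect be?** Three inputs, all assumptions:
- p = success rate among subjects observed at the visit
- d = fraction missing at the visit
- f = share of the missing who left as non-responders; the rest are taken to respond at rate p

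Rate in all subjects = p(1 − d) + d(1 − f)p + d·f·0 = p − p·d·f. The overstatement is therefore p × d × f.

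With p = 50% and d = 20%:

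| f | p × d × f | Overstatement | Rate in all subjects |
|---|---|---|---|
| 0% | 0.50 × 0.20 × 0 | 0 points | 50% |
| 25% | 0.50 × 0.20 × 0.25 | 2.5 points | 47.5% |
| 50% | 0.50 × 0.20 × 0.50 | 5 points | 45% |
| 100% | 0.50 × 0.20 × 1 | 10 points | 40% |

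Check by counts, taking the planned total of 300 + 100 = 400: 20% missing leaves 320 observed, of whom 160 succeed (50%). If 40 of the 80 missing left as non-responders and the other 40 respond at 50% (20 successes), the rate is (160 + 20)/400 = 45%. If all 80 are non-responders it is 160/400 = 40%.

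**Range.** With f = 100%, the overstatement runs from 0.30 × 0.10 = 3 points to 0.60 × 0.40 = 24 points over p = 30–60% and d = 10–40%. Counting every missing subject as a non-responder gives p(1 − d), a lower bound. At p = 50% that is 45%, 40%, 35% and 30% for d = 10%, 20%, 30% and 40%.

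**Opposite direction.** If all the missing were responders, the rate at p = 50% and d = 20% would be 0.50 × 0.80 + 0.20 = 60%, so the as-observed figure would be too low.

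**The case against.** The best defence has five parts.

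- **Tallying is left to the SAP.** Section 10.5 says so, and Section 11.1 leaves the denominator open. This stands in part: restriction to attending subjects is the natural reading of as observed, not a stated denominator. But Section 11.1 already fixes that missing efficacy data stay missing, and a SAP that counted withdrawn subjects as failures would be hard to square with it.
- **Withdrawal for ineffectiveness is discretionary.** It is also absent from the Section 9.6.3 list. This stands. A reader might infer that long-term response *is* overstated as a built-in result of the rule. The documents do not support that: no dropout figures exist, and the effect is zero if f = 0. Subjects who clear may stop treatment (Section 10.8); if some of them stop attending, the bias could run the other way.
- **Early termination assessments exist.** They do, but no stated rule assigns them to a scheduled visit. If one did, each would fill a single visit and later visits would stay missing.
- **A reader can recover much of this.** Section 11.3 promises numbers and percentages, so the number observed can be worked back and the successes divided by the reported Safety Population. That gives a rough lower bound for IGA and mPASI-75. It does not work for I-IGA, which is recorded only in subjects with a Day 1 score of at least 2 (Section 10.2.1), and it does not separate reasons for leaving.
- **This is a safety study.** The efficacy summaries are descriptive and the IGA endpoint is openly labelled as observed. This stands, and limits the weight of the point.

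**Conclusion.** The point holds in conditional form. The protocol leaves missing responder data missing and also permits exits related to non-response, so late IGA, I-IGA and mPASI-75 success rates are liable to upward bias. The size is about p × d × f: nil if no one leaves as a non-responder, 5 points at p = 50%, d = 20%, f = 50%, and 10 points at f = 100%. All three values are assumed, and the formula takes the remaining missing subjects to respond like those observed.

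The documents do not show that bias will occur, nor that every dropout is a failure. No test, error rate or primary safety conclusion is affected. A supportive analysis is nonetheless worth adding, because these are listed secondary endpoints that may be read as evidence of durability.

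**What to change.** 1. Keep the as-observed table. At each visit show the number observed beside the number dosed in ARQ-151-202. For I-IGA, the reference number should be subjects with a Day 1 I-IGA of at least 2; an all-dosed denominator would count people without intertriginous disease as failures.
2. Add a supportive table for the three endpoints in which subjects withdrawn for lack of efficacy, an adverse event or prohibited psoriasis therapy count as non-responders at all later visits. State explicitly how subjects missing for other reasons are treated, for example by also showing all missing as non-responders as a lower bound. Amend the Section 11.1 sentence on missing data so that it permits this.
3. State whether early termination assessments are assigned to a scheduled visit and, if so, by what rule.
4. Reconcile the Synopsis provision on ineffective treatment with the removal list in Section 9.6.3, so that reasons for withdrawal are recorded consistently.

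Cost: one further set of tables from efficacy and withdrawal data already collected, and some protocol wording. The supportive rate will probably look less favourable than the as-observed one.
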